#### 11.5.2 Determination of tissue proliferative index

*Proliferative Index* will be determined using an immunohistochemistry (IHC) assay to evaluate Ki-67 expression from epithelial cells contained in RPFNA samples. A categorical estimate of the number of ductal epithelial cells present on the slides designated for proliferative index evaluation will first be assessed: less than 100, 100 to 500, 500 to 1,000; 1,000 to 5,000; or more than 5,000. Slides containing at least 100 epithelial cells will be processed for Ki-67 staining; if no slides meet this criterion, the subject will be deemed unevaluable for this endpoint at that time point. Antigen retrieval will be performed with 10 mmol/L citrate buffer (pH 6) and then will be stained with Ki67 clone MiB-1 monoclonal antibody (Dako North America, Carpinteria, CA) at a 1:20 dilution. Hyperplastic cell clusters will be preferentially assessed for nuclear staining. The number of cells with unequivocal nuclear staining out of 500 cells assessed will be recorded

as the proliferative index. Slides will be hand scored by two readers as described in Section 11.5.1, and in the case of a difference between the two readers, the scores will be averaged. Agreement between two readers using this method is excellent (Cronbach's  $\alpha = 0.99$ ; reported in [86]). Within-person reliability is also superb, with a previously reported intraobserver variance of 4% [100].

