**Cytomorphology and proliferative index.** Samples for cytomorphology and proliferative index will be collected at two time points, at pre-treatment (t0) and at post-treatment (t2). The Masood score for cytomorphology ranges from 6 to 24, which can be classified into 4 groups of worsening morphology: 1) nonproliferative (6-10), 2) hyperplasia without atypia (11-14), 3) hyperplasia with atypia (15-18), 4) malignancy (19-24). A patient is considered to have cellular atypia if their Masood score is 15 or above. We will compare the effects of low dose tamoxifen versus placebo on changes in Masood score between pre- and post-treatment. Masood score will be treated as a continuous variable, transformed to normality as appropriate, and the linear mixed effects model applied using an indicator variable for pre- and post-treatment time points. We will also consider Masood score as an ordinal outcome with 4 categories and as a dichotomous outcome (cellular atypia or not), and apply the generalized linear mixed model (GLMM) for non-normal data [105].

Proliferative index, defined as the number of cells with unequivocal nuclear staining (Ki-67 expression) out of a total number of ductal epithelial cells contained in RPFNA samples, will be analyzed using longitudinal logistic regression with two time points. If cell counts are better approximated by a Poisson distribution, we will apply the longitudinal Poisson regression method.

**Insulin growth factors.** Insulin growth factor-1 (IGF1) and insulin growth factor binding protein-3 (IGFBP3) will be treated as continuous measures. We will apply the linear mixed effects model for between group comparisons of measures from the three time points. The unstructured mean model and linear in time model will be employed.

***Aim 2:** To establish safety and tolerability of low-dose tamoxifen.*

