The presence/absence of gynecological symptoms (for each symptom mentioned above) will be compared between treatment groups using 2x2 tables using the Fisher exact test, stratified on CYP2D6 status. Logistic regression will be used to compare the frequency between treatments adjusted for covariates, including CYP2D6. Longitudinal analysis also will be conducted to compare the trends of the presence/absence of each of the reported gynecological symptoms over the 2 year period using the generalized linear mixed-effects model for binary outcomes.

For each liver function measure, a woman will be considered to have elevated liver function if the measurements at years 1 and/or 2 are above the upper limit of the institutional reference range and higher than her baseline pre-treatment level. These data will be coded such that those who are greater than 2-times the upper limit of the reference range will be considered to be clinically significant (grade 1 if asymptomatic and requiring no intervention; grade 2 if minimal/local/non-invasive intervention required). The frequency of women with elevated liver function measures will be compared between treatment groups using an exact test on 2x2 tables, stratified on CYP2D6. Logistic regression analysis will also be used to compare the frequency of elevated liver function between treatments, adjusted for covariates. Linear mixed-effects model for normally distributed data will also be used to compare the trends in liver function levels between the treatment groups. Procs MIXED and GLIMMIX will be used for longitudinal analysis of normally and non-normally distributed data, respectively. Poisson regression analysis will be conducted using Proc GENMOD, all in SAS 9.1 (Cary, North Carolina).

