Tissue and blood biomarkers: Masood score (cytomorphology) and Ki67 expression (proliferative index) evaluated from breast tissue samples will be obtained at t0 and t2. Insulin growth factors (IGF1 and IGFBP-3) will be measured at 3 time points. With a baseline sample size of 115 women per arm (assuming 10% yearly attrition), assuming Type I error=0.05, 2-sided test, and a within-person correlation of 0.5 between pairs of normally distributed measurements, there is 80% power to detect an effect size of 0.34 (absolute difference between treatment and control means divided by the common standard deviation) at year 2. A similar effect size is detectable for Ki67 for which the problem was formulated as that of detecting the difference at t2 in percent of women with positive expression (at least one cell expressing Ki67) between the treatment groups. Kahn et al [86] reported a median Ki67 expression level of 1.4% in RPFNA samples collected from 147 women at high risk for breast cancer. Thus, we hypothesized that 50% (conservative estimate) to 85%.of our cohort will have Ki67 expression in their healthy breast tissue samples collected via RPFNA at their baseline visit.

Detectable values for the various outcomes are shown in the table below. Column 2 shows the assumed common mean ( $\pm$  SD) at t0 for both treatment groups (obtained from the literature, adjusted for the age structure of our cohort, if possible). Column 3 shows the minimum detectable level at t2 for the tamoxifen group in the hypothesized

direction. The mean levels at t2 in the placebo group are assumed to remain the same as those at t0. Column 4 shows the detectable % change at t2 relative to t0 in the tamoxifen group.

Outcome	Assumed levels at t0 for Placebo and Low dose Tamoxifen groups	Detectable levels at t2 (80% power) for Low dose Tamoxifen group	
	Mean ± SD	Mean	% change (from t0)
Masood score 	14 ± 1.8	13.4	4% ↓
Women positive for Ki67 expression  (%)	50%	32%	36% ↓
	65%	47%	28% ↓
	85%	70%	18% ↓
IGF1  (ng/ml)	260 ± 82.5	230	12% ↓
IGFBP-3  (ng/ml)	3346 ± 1226	3787	13% ↑

Thus, we expect to be able to detect a 5-36% difference in the BC risk biomarkers proposed as secondary endpoints.

**Aim 2:** *To establish safety and tolerability of low-dose tamoxifen.*

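### Ki67 is analysed on cells with no stated allowance for slide-to-slide variation within a woman, and its quoted power belongs to a woman-level test that the analysis plan does not list

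*Combined protocol and SAP*

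**What the plan says.** **Analysis (12.4, Aim 1, cytomorphology and proliferative index).** The index is the number of stained cells over the number of ductal epithelial cells in the RPFNA sample. It "will be analyzed using longitudinal logistic regression with two time points. If cell counts are better approximated by a Poisson distribution", the Poisson version is used. Section 12.4 judges secondary efficacy endpoints by the time-by-group interaction. For software, the end of 12.4 says only that "Procs MIXED and GLIMMIX will be used for longitudinal analysis of normally and non-normally distributed data, respectively". No random terms are given for Ki67. For pill counts, which are also counts out of a total, 12.4 does name random-intercept and random-intercept-and-slope models.

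**Sizing (12.5, tissue and blood biomarkers).** The setting is: "With a baseline sample size of 115 women per arm (assuming 10% yearly attrition), assuming Type I error=0.05, 2-sided test", with "a within-person correlation of 0.5 between pairs of normally distributed measurements". From this, "there is 80% power to detect an effect size of 0.34". Ki67 is then treated separately, as the difference at year 2 "in percent of women with positive expression (at least one cell expressing Ki67) between the treatment groups". The detectable pairs are 50% vs 32%, 65% vs 47% and 85% vs 70%.

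**Measurement (11.2 and 11.5.2).** All of a woman's aspirates at a visit are pooled into one tube. Stained cells are counted out of 500, slides with at least 100 cells are accepted, and "Hyperplastic cell clusters will be preferentially assessed for nuclear staining". RPFNA was dropped for new patients with protocol version 3/9/2015 and for everyone from 10/26/15.

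**The concern.** The woman is randomised, and she gives one pooled sample before treatment and one after. A random intercept per woman removes only what her two slides share. Given that intercept, a plain binomial or Poisson model treats the hundreds of cells on a slide as independent observations.

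Her two slides can differ for reasons other than counting noise: different aspirates, preferential reading of hyperplastic clusters, and biological change over two years. That variation falls directly on the time-by-treatment contrast, and such a model leaves it out of the standard error. Switching from logistic to Poisson does not help, because at an index near 1.4% the two almost coincide.

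Two things are at stake. The first is the error rate of an endpoint that section 2.4 describes, with cytomorphology, as the only direct measure of breast tissue response. The second is that a reader of 12.5 will attach 80% power to an analysis for which it was not calculated.

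**Working it through.** **1. The plan's own power.** Two-proportion test, two-sided 5%, 1:1:

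z = [d − 1.96·√(2p̄(1−p̄)/n)] / √([p₁(1−p₁)+p₂(1−p₂)]/n), power = Φ(z).

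For 50% vs 32% at n = 115: p̄ = 0.41, and the two standard errors are 0.0649 and 0.0638. Then z = (0.18 − 1.96×0.0649)/0.0638 ≈ 0.83, so power is 79.7%.

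| Pair | 115 per arm | 94 per arm |
|---|---|---|
| 50% vs 32% | 79.7% | 71.2% |
| 65% vs 47% | 78.9% | 70.4% |
| 85% vs 70% | 78.1% | 69.5% |

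The stated 80% is recovered within 2 points when all 115 women are used. The figure of 94 is the number of completers that 12.5 uses for adverse events.

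**2. Inputs for the error rate.** From the documents: median index 1.4% (12.5), 500 cells read and a minimum of 100 (11.5.2), 94 per arm (12.5), time-by-group test (12.4). Assumed: logit-normal indices, between-woman SD 1.0 (1.4 in the last row), and a slide SD within a woman from 0 to 1.4 on the logit scale.

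**3. Why fewer women do not help.** For a woman at the median, the counting variance of one slide's log-odds is about 1/(500×0.014×0.986) = 0.145. A slide SD of 0.5 adds 0.25, which the model omits. The true standard error is then √(1 + 0.25/0.145) ≈ 1.65 times the reported one. The number of women cancels from this ratio. It alone turns 5% into 2[1 − Φ(1.96/1.65)] ≈ 24%. The simulated rates are higher because women with high indices carry most of the cell counts.

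**4. Simulated null trials.** Cell-level test, woman random intercept only, nominal 5%, 500 cells, 3,000 trials per setting. The last column is a full random-intercept logistic model with a likelihood-ratio test, 400 trials per setting.

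| Slide SD | 94 per arm | 20 per arm | Full model, 94 per arm |
|---|---|---|---|
| 0 | 4.3% | 4.5% | 3.8% |
| 0.2 | 14.7% | 14.1% | not run |
| 0.3 | 24.6% | 21.4% | 27.8% |
| 0.5 | 44.1% | 43.7% | 46.8% |
| 0.7 | 59.3% | 57.6% | not run |
| 1.0 | 72.7% | 69.3% | 73.0% |
| 1.4 | 80.7% | 80.5% | not run |

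With 100 cells and 94 per arm the rate is 16.4% at slide SD 0.5, 44.2% at 1.0 and 59.5% at 1.4. The Poisson form at 500 cells agrees: 25% at 0.3, 45% at 0.5 and 81% at 1.4.

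**5. Alternatives in the same null setting.** A t-test on the within-woman change in empirical logit gives 4% to 6%. The woman-level any-positive test at year 2 gives 3.9% to 5.6% at 94 per arm. Woman-clustered robust errors give 5.7% to 6.8% at 94 per arm, but 8% to 14% at 20 per arm.

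**The case against.** **The plan is silent; it does not commit to the wrong model.** Every inflated figure comes from a model with a random intercept only, and 12.4 does not say that this is the model. A slide-level random effect or clustered robust errors would fit the same words. The pill-count text shows that the authors know richer random-effects models. This stands, and it makes the error rates conditional. It does not dispose of the point: the only alternatives 12.4 names are binomial and Poisson. A conventional fit of either is exposed, and the text leaves a valid or an invalid fit to be chosen after the data are seen.

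**A stronger reading is tempting but unsupported.** A reader might infer that the Ki67 test will be falsely positive in most null trials. At an index of 1.4%, 0.986^500 = 0.0009, so 99.9% of 500-cell slides would be positive if all women were alike, yet 12.5 assumes 50% to 85%. Under a logit-normal form, 85% positive implies a total SD of about 2.11. A correlation of 0.5 then gives a slide SD of 2.11×√0.5 ≈ 1.5, in the 80% region. But the first step shows only total spread, and a random intercept absorbs the between-woman part. The 0.5 is stated for normally distributed measurements, not for Ki67 on the logit scale. A rate above 50% needs a slide SD above about 0.6 at 500 cells, or between 1.0 and 1.4 at 100 cells. No document gives that SD, and pooling several aspirates should reduce part of it.

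**Sizing on a simpler summary is not in itself an error.** Section 12.5 does the same for breast density. That is fair, and a baseline-adjusted comparison with correlation 0.5 would give about 82% to 84% with 94 women. But 12.4 lists no woman-level Ki67 test, adjusted or not.

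**The consequence is limited.** Ki67 is secondary, and RPFNA was stopped. Both are true, but the inflation persists for the women already sampled.

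**Conclusion.** The point holds as a conditional one. Ki67 is analysed on cells with no stated variance allowance, and its quoted power describes a woman-level test that 12.4 does not plan.

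With a woman random intercept only and 500 cells per slide, the false-positive rate runs from about 4% (slide SD 0) through about 25% (0.3) and about 45% (0.5) to about 80% (1.4). It is much the same at 20 women per arm. These figures rest on an assumed slide SD, logit-normal indices and that choice of model. Even an SD of 0.2 to 0.3 gives three to five times the nominal rate.

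On power, the unadjusted figure is 78% to 80% with 115 per arm and about 70% to 71% with 94. The number of evaluable pairs after RPFNA was stopped is not given and could be much smaller. The plan should be changed, although the trial's primary conclusion does not depend on it.

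**What to change.** **In 12.4,** name the woman's sample at each visit as the unit of analysis for Ki67. Either add a woman-by-visit random effect to the logistic model, use a beta-binomial model, or compare the within-woman change in empirical-logit index between arms. The last is preferable if few pairs exist. Use woman-clustered robust GEE only with a small-sample correction. Remove the plain binomial and Poisson options.

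**In 12.5,** do one of two things. List the any-positive-cell test by woman at year 2 as a planned analysis, with its power restated for the women who have evaluable samples. Or tie the Ki67 power statement to the revised analysis.

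**Cost.** A short change to the text and one more model term. The confidence interval for Ki67 will be wider and the stated power less favourable. No new data are needed.

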**Objective safety measures:**

**Adverse events.** The number of grade 2-4 toxicities observed will be tabulated by treatment arm. Differences by treatment arm will be evaluated using Fisher exact tests.

**Biomarkers.** Total cholesterol, low and high density lipoprotein, triglycerides, anti-thrombin III enzymatic assay (for clotting propensity), and serum bone-specific alkaline phosphatase (BSAP, for bone formation) and urine N-telopeptides (NTX, for bone resorption) measurements will be treated as continuous variables. Transformed to normality as appropriate, the linear mixed effects model will be applied, using the unstructured mean model using and linear in time model, to assess the effects of low dose tamoxifen on these measurements over time.

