## 6.0 DOSE SCHEDULE AND RULES FOR TREATMENT DISCONTINUATION

### 6.1 Dose Schedule

Randomization will be stratified according to the rules outlined in Section 12.3. Subjects will be randomized 1:1 to receive low-dose tamoxifen 5 mg or placebo daily for 24 months. Registration will be done via a central database, Interactive Web Response System (IWRS), which will also perform stratified treatment assignment. This system is maintained by Sharp Clinical Services, which is separate from the coordinating center and all participating sites such that all study staff (except for the statistician when preparing reports for the DSMB) will remain blinded.

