### 8.2.2 Adverse Events: List and Reporting Requirements

Adverse event (AE) monitoring and reporting is a routine part of every clinical trial. Serious Adverse Events (SAEs) are reported by the site PI within 24 hours to the coordinating center ([[contact]](mailto:[contact]), [contact]). The Coordinating Center is then responsible for reporting SAEs to the UAB IRB and Clinical Trials Monitoring Committee in accordance with study-specific requirements. SAEs occurring at participating sites are reported to the UAB IRB as “non-UAB” events.

A Serious Adverse Event (SAE) is an AE that 1) results in patient hospitalization or prolongation of hospitalization; 2) results in persistent or significant disability or incapacity; 3) results in death; 4) is a cancer or congenital abnormality or 5) results in the development of drug dependence or abuse. An AE must be considered an SAE when the nature or severity of the event is not consistent with the current Investigator’s Brochure. Participating site SAEs must be reported by the site PI to the coordinating center as described above. It is also the responsibility of the site PI to report SAEs to the site IRB and to submit copies of that report to the coordinating center. It is the Coordinating Center’s responsibility to report the SAE to the appropriate regulatory agency and / or industry sponsor. This submission of IND Safety Reports will be cross referenced according to local regulations to Onyx Investigational Compound Number (IND) at the time of submission.

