**Adverse events:** We assume the rate of grade 2-4 toxicities in the placebo group to be low, at 0.5%. At the end of the study, with 94 women in each arm (accounting for 10% attrition per year), the study will have at least 80% power to detect an adverse event rate of 9.1% in the low dose tamoxifen group based on Fisher’s exact test and Type I error=0.05.

**Adherence to therapy:** We will examine the difference in adherence rates of the treatment groups by comparing the percent of pills taken across 8 time points. With 115 women at baseline per arm, assuming a constant adherence rate of 90% in the placebo group and a between-measurement correlation of 0.6 and 2-sided alternative, there will be 80% power to detect an adherence rate of about 77% in the low dose tamoxifen group.

**Voluntary withdrawals:** If the proportion of patients in the placebo arm who withdraws voluntarily by the end of the study is 10%, then with 115 women in each arm at baseline, assuming type I error=0.05, the study will have 80% power to detect a significant difference in the voluntary withdrawal rate in the low dose tamoxifen group if the withdrawal rate in the intervention group is about 28%.

**Safety biomarkers:** We focus here on total cholesterol (TC), anti-thrombin-III (AT-III), bone-specific alkaline phosphatase (BSAP), and urine N-telopeptide crosslinks (NTX). With the proposed sample sizes, the detectable effect size (described earlier) is 0.34. A relatively small % change in mean levels is detectable for TC and AT-III but larger % changes are needed to detect a significant treatment difference at t2 for BSAP and NTX.

Outcome	Assumed levels at t0 for Placebo and Low dose Tamoxifen groups	Detectable levels at t2 (80% power) for Low dose Tamoxifen group	
	Mean ± SD	Mean	Relative % change (from t0)

TC* (mg/dL)	199 ± 45	214.3	8% ↑
AT-III** (%)	100 ± 13.3	95.5	5% ↓
BSAP  (µg/L)	7.7 ± 4.5	6.2	20% ↓
NTX  (nM BCE/mM)	24.4 ± 16.1	18.9	23% ↓

\* Mean obtained from [111], sd obtained from [112]

\*\* per ARUP reference laboratory

Thus, we expect to be able to detect a 5-23% difference in the objective safety biomarkers proposed as secondary endpoints.

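### The Aim 2 adverse-event comparison stops at grade 4, so a woman whose only qualifying toxicity is fatal is not counted in it, and Section 12 plans no table of deaths by arm

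*Combined protocol and SAP*

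**What the plan says.** Section 12.4, Aim 2, under adverse events, has two sentences: "The number of grade 2-4 toxicities observed will be tabulated by treatment arm", and "Differences by treatment arm will be evaluated using Fisher exact tests".

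Section 12.5, Aim 2, powers the same comparison on the same grades: "We assume the rate of grade 2-4 toxicities in the placebo group to be low, at 0.5" per cent. It then states that "the study will have at least 80% power to detect an adverse event rate of 9.1% in the low dose tamoxifen group", "with 94 women in each arm (accounting for 10% attrition per year"), using Fisher's "exact test and Type I error=0.05".

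Death appears elsewhere in the protocol:

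- Section 6.3 prints a five-grade scale for thrombosis/embolism in which grade 5 is death. It also lists death among the reasons for ending protocol therapy.
- Section 8.2.2 includes death in the definition of a serious adverse event: "3) results in death; 4) is a cancer or congenital abnormality". Section 6.3 has such events sent to the coordinating center within 24 hours, for onward reporting to the IRBs and the DSMB.
- Section 10.0 promises that the toxicity outcome of all eligible subjects will be reported, but gives no method.
- Section 12.4, Exploratory Aim 2, compares new cancers, thromboembolic events and cataract between arms by Fisher's exact test and Poisson regression, with no grade limit.

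**The concern.** Fatal toxicity has its own grade on the protocol's printed scale, and the Aim 2 count ends one grade below it. No section says that a fatal event is also recorded at grade 4. A woman with no other grade 2-4 toxicity who dies of a toxicity therefore adds nothing to the count. If that death was caused by the drug, leaving it out moves the comparison towards no difference.

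The deaths are collected, but Section 12 does not ask for them to be tabulated by arm. A reader of the end-of-study safety analysis would have to look for them in the serious-event reports.

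There is also a small mismatch of unit. Section 12.4 speaks of a number of toxicities, while Section 12.5 speaks of women. Fisher's test on a two-by-two table needs one entry per woman.

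**Working it through.** **Inputs.** Placebo rate 0.5%, tamoxifen rate 9.1%, 94 women per arm, type I error 0.05, Fisher's exact test (all 12.5); 1:1 allocation (6.1). The sidedness of this test is not stated.

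**Step 1: the plan's own figures.** Women per arm after two years: 115 × 0.9 × 0.9 = 93.15, rounded up to 94. Expected women with an event: 94 × 0.091 = 8.6 on tamoxifen and 94 × 0.005 = 0.5 on placebo. The stated power is at least 80%. Recomputed at 94 per arm:

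| Method | Power |
|---|---|
| Normal approximation, two-sided | 79.2% |
| Fisher exact, one-sided (full enumeration) | 85.7% |
| Fisher exact, two-sided (full enumeration) | 75.4% |

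The claim is met by a one-sided Fisher test and nearly met by the normal approximation. It is not met by a two-sided Fisher test. That is a separate matter from the grade limit.

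**Step 2: which fatal events are missed.**

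| Fatal event | Aim 2 comparison (grades 2-4) | Exploratory Aim 2 (no grade limit) |
|---|---|---|
| Pulmonary embolus, stroke | not counted | counted |
| Uterine or other cancer | not counted | counted |
| Cardiac infarction (named in 6.3) | not counted | not listed |
| Hepatic necrosis (named in 3.3) | not counted | liver tests only, at baseline and years 1 and 2 |

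In every row, a woman who also has a grade 2-4 toxicity on record is still counted in Aim 2. Exploratory Aim 2 counts that the event occurred, not that it was fatal, so neither analysis yields deaths by arm. The protocol prints the scale for one category only; that other categories also have a fatal grade 5 is an assumption.

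**Step 3: how much a death can move the test.** With k women against 0 in equal arms of 94, the two-sided Fisher p-value is 2 × C(94,k) / C(188,k):

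| k against 0 | 1 | 2 | 3 | 4 | 5 | 6 |
|---|---|---|---|---|---|---|
| p | 1.00 | 0.50 | 0.25 | 0.12 | 0.059 | 0.029 |

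Deaths alone would have to reach 6 against 0 before p fell below 0.05. A death added to non-fatal events matters only at the boundary: 5 v 0 gives 0.059 and 6 v 0 gives 0.029; 7 v 1 gives 0.065 and 8 v 1 gives 0.035.

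**Step 4: sensitivity to the fatal share.** The documents do not say what share f of tamoxifen-arm events would be fatal with no other grade 2-4 record, so f is an assumption. The counted rate becomes 0.091 × (1 − f). Two-sided Fisher power at 94 per arm:

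| f | 0% | 5% | 10% | 20% | 50% |
|---|---|---|---|---|---|
| Power | 75.4% | 71.0% | 66.2% | 55.2% | 18.0% |

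Shares of 10% and 20% correspond to 8.6 × 0.1 = 0.9 and 8.6 × 0.2 = 1.7 expected deaths.

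**Step 5: how many deaths to expect.** Section 3.3 gives 0.8 pulmonary emboli and 1.4 strokes per 1000 women per year at 20 mg. Without attrition, the tamoxifen arm has 115 × 2 = 230 woman-years. That gives 0.8 × 0.230 = 0.18 emboli and 1.4 × 0.230 = 0.32 strokes, fatal and non-fatal together. The documents give no rate for other fatal toxicities.

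**The case against.** The strongest reply is that deaths are not overlooked. They are serious adverse events reported within 24 hours. The monitoring committee that serves as the central DSMB reviews adverse reactions monthly (8.2.3). Exploratory Aim 2 would also count a fatal embolus, stroke or cancer by arm. All of this stands. A reader might infer from the grade limit that no analysis in Section 12 counts a fatal event, or that a lethal drug effect could pass as no effect in the trial as a whole. The documents do not support either inference. What remains is that serious-event reporting is not a planned between-arm analysis, and that Exploratory Aim 2 neither covers every fatal toxicity nor counts deaths.

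A second reply is that the p-value pairs in Step 3 sit on the significance boundary, where one event of any grade changes the result. That is right. A reader might infer that one uncounted death would decide the test, but the pairs say nothing about how likely such a death is, and Step 5 suggests that thromboembolic deaths would be rare.

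A third reply concerns the unit. A reader might infer that repeat toxicities in one woman would enter the table separately and make the Fisher test invalid. No section says so, and Section 12.5 works with 94 women per arm. The wording of 12.4 is loose, but 12.5 largely settles the intent.

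**Conclusion.** The point holds in a limited form. As written, the Aim 2 comparison and its power statement omit a woman whose only qualifying toxicity is fatal, and Section 12 plans no table of deaths by arm. The omission is confined to this comparison. Fatal toxicities outside the thromboembolic and cancer categories have no other planned by-arm count.

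The numerical effect is likely small. One or two deaths against none would not approach significance even when counted, and the documented thromboembolic rates imply less than one embolus or stroke in the tamoxifen arm (0.18 + 0.32 = 0.50). The power losses in Step 4 depend wholly on assumed fatal shares and are not forecasts. The gain from correcting the text is mainly a complete and readable safety report.

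This rests on reading the grade range literally and on a fatal event being recorded at grade 5 only.

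**What to change.** In 12.4, Aim 2, replace the count of grade 2-4 toxicities with the number of women whose worst toxicity is grade 2 or higher (grades 2 to 5). Compare that number between arms with the Fisher exact test, with the woman as the unit, as 12.5 already assumes. Add a listing of deaths by arm, cause and attribution. Use the same endpoint definition in the 12.5 power statement, and state there whether the test is one- or two-sided.

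The cost is a few sentences in two sections. Deaths are already collected, so no new data are needed. Power at the planned 9.1% against 0.5% does not change, because only the definition of the event is completed.
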